We will use the ultrasound pulse parameters used by Cain et al ³⁹ for sonication of the globus pallidus (see previous paragraph) because their experiment demonstrated hemodynamic effects without adverse effects in healthy subjects and the stimulation parameters were very low-intensity and extremely low risk. If we do not see effects on functional connectivity or symptoms after the first 5 participants and if the single sessions are well-tolerated, we will switch to repeated dosing, applying three PLIFUS or sham sonifications over 5 days since repeated exposures may be required to produce detectable effects. A single session of PLIUS will include 5 minutes net total dosage of PLIFUS. The exposure uses ten 30 sec blocks of PLIFUS sonication with 30 sec rests in-between spread over ten minutes. Sonication will be delivered (Fig. 3) in low-amplitude pulses using a carrier wave frequency: 361 kHz, pulse repetition frequency: 100 Hz, and duty cycle: 5 % yielding an I_{spta} 1.5 W/cm² at the Gpi. The acoustic intensity used is in the range of FDA and Electrotechnical Technical Commission (ETC) regulation standards for diagnostic and therapeutic ultrasound, respectively ²⁸.

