2.4 Potential Risks & Benefits

2.4.1 Known Potential Risks

Risks of PLIFUS:

Because ultrasound has been used extensively for many years as a diagnostic tool in other fields of medicine, FDA safety regulations are well-established and well-validated. Some investigations of brain sonication have exceeded these safety guidelines and have not produced serious adverse effects. Theoretical adverse effects at very high levels of energy, far in excess of what will be used in this trial, include injury to brain tissue (lesions, bleeding, disruption of the blood-brain barrier) due to excessive heating or cavitation. In 704 human subjects who have been studied in 35 trials of transcranial ultrasound, no serious adverse events have been reported. Mild and transient side effects have been reported in 3.3% of subjects, including headache, neck stiffness, worsening mood, scalp heating, muscle twitches, cognitive effects (impaired attention), itchiness, sleepiness and anxiety⁴³. Rates of side effects associated with sham sonication have not been reported. The sonication parameters that will be employed adhere to FDA and ETC regulation standards for diagnostic and therapeutic ultrasound²⁸.

While PLIFUS is associated with only mild and transient side effects in healthy participants, it has not previously been studied in schizophrenia. It is possible that sonication of the Gpi might worsen symptoms of schizophrenia. If this happens, we expect it to be a transient effect, consistent with other behavioral effects. To minimize this risk, we will exclude from study individuals with a history of violence, aggression or suicidal behavior. We will be monitoring the severity of psychotic symptoms during sonication and will stop the procedure if symptoms worsen by more than 50% on AHRS and DESA or if the participant expresses clinically significant psychological distress or suicidal ideation. The study psychiatrist will remain with the participant during sonication and for 1 hour after completion of sonication to assess for worsening of psychosis and suicidality. The study psychiatrist will arrange for appropriate monitoring and further assessment after 1 hour if needed based on clinical judgement.

Risks of MRI:

A total of 7 MRIs will be performed using a Siemens 3T Prisma; one prior to the intervention visits and one preceding

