6.1.7 Starting Dose and Dose Escalation Schedule

The starting dose will be a single session following the parameter specified above (see Dosing and Administration). If an effect on functional connectivity or symptoms is not detected in the first 12 completers, the dose will be changed to three administrations spaced over 5 days using the same sonication parameters for 4 additional participants.

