7.11 Classification of an Adverse Event

7.11.1 Severity of Event

For AEs not included in the protocol defined grading system, the following guidelines will be used to describe severity.

- **Mild** – Events require minimal or no treatment and do not interfere with the participant's daily activities.
- **Moderate** – Events result in a low level of inconvenience or concern with the therapeutic measures. Moderate events may cause some interference with functioning.
- **Severe** – Events interrupt a participant's usual daily activity and may require systemic drug therapy or other treatment. Severe events are usually potentially life-threatening or incapacitating.

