7.11.2 Relationship to Study Agent

The research psychiatrist's assessment of an AE's relationship to sonication/sham is part of the documentation process, but it is not a factor in determining what is or is not reported in the study. If there is any doubt as to whether a clinical observation is an AE, the event should be reported. All AEs must have their relationship to study agent assessed. In a clinical trial, the study product must always be suspect. To help assess, the following guidelines are used.

- **Related** – The AE is known to occur with the study agent, there is a reasonable possibility that the study agent caused the AE, or there is a temporal relationship between the study agent and event. Reasonable possibility means that there is evidence to suggest a causal relationship between the study agent and the AE.
- **Not Related** – There is not a reasonable possibility that the administration of the study agent caused the event, there is no temporal relationship between the study agent and event onset, or an alternate etiology has been established.

For all collected AEs, the research psychiatrist who examines and evaluates the participant will determine the AE's causality based on temporal relationship and his/her/their clinical judgment. The degree of certainty about causality will be graded using the categories below.

- **Definitely Related** – There is clear evidence to suggest a causal relationship, and other possible contributing factors can be ruled out. The clinical event, including an abnormal laboratory test result, occurs in a plausible time relationship to drug administration and cannot be explained by concurrent disease or other drugs or chemicals. The response to withdrawal of the drug (dechallenge) should be clinically plausible. The event must be pharmacologically or phenomenologically definitive, with use of a satisfactory rechallenge procedure if necessary.
- **Probably Related** – There is evidence to suggest a causal relationship, and the influence of other factors is unlikely. The clinical event, including an abnormal laboratory test result, occurs within a reasonable time after administration of the drug, is unlikely to be attributed to concurrent disease or other drugs or chemicals, and follows a clinically reasonable response on withdrawal (dechallenge). Rechallenge information is not required to fulfill this definition.

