7.14 Study Halting Rules

Administration of PLIFUS will be halted if three grade 3 AEs determined to be "probably related" are observed. [name] will inform the DSMB members within 24 hours of this occurrence and will provide the DSMB with AE listing reports. The DSMB will convene an ad hoc meeting by teleconference or in writing as soon as possible. The DSMB will provide recommendations for proceeding with the study. If the study is conducted under an IDE, [name] will inform the FDA of the temporary halt and the disposition of the study.

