addition to all adverse events recorded by the SAFTEE assessments, the DSMB will receive a report of any additional participant complaints, instances of participant distress, or breaches of confidentiality. Because this is a pilot study with a very small sample size, formal statistical criteria are not identified in advance for a stopping rule. The DSMB may halt the study for reasons of safety—we are not aware of any significant safety concerns. The DSMB must approve the decision to switch from one session of PLIFUS to 3 sessions if no effect is detected after the first 12 completers with good quality imaging data. A failure to detect an effect size of 0.5 or greater compared to sham on the AHRS, DESA, and PSYRATS total score or on GPi functional connectivity after the first 12 participants will define “no effect” and trigger a switch to 3 treatment sessions over 5 days for phase II of the study which will involve an additional 4 participants. The DSMB will also be provided copies of all communications with the IRB. The DSMB will meet prior to initiation of the study and a minimum of every six months and will be provided data regarding enrollment and side effects and a study summary prior to each meeting. [name] and study staff will not attend the closed section of the DSMB meetings. Throughout the study, notification of any Serious Adverse Events (SAEs) as well as any proposed investigator-initiated changes in the protocol will be submitted to the DSMB. Based on its review of the revised protocol, the DSMB will identify the data parameters and format of the information to be regularly reported. All SAEs and adverse events will be tabulated and submitted to the IRB and DSMB in the bi-annual (every 6 months) data reports or at the time of continuing review. AEs will be reported to the IRB annually (at continuing review) if they are expected, related, and harmful. A summary of the outcomes of the safety reviews as prepared for the DSMB along with accumulated adverse events and deviations will be submitted to the IRB as part of an annual progress report at the time of the Continuing Review submission.

8 Clinical Monitoring

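### Read literally, the only numeric halting trigger leaves out definitely related events and uses a severity label the protocol does not define; separately, two causality thresholds for prompt IRB reporting conflict

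*Combined protocol and SAP*

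**What the plan says.** **Halting.** Section 7.14 reads: "Administration of PLIFUS will be halted if three grade 3 AEs determined to be 'probably related' are observed". The DSMB is then told within 24 hours, meets ad hoc and advises on how to proceed. Section 7.15 adds that "formal statistical criteria are not identified in advance for a stopping rule", so 7.14 is the only study-level trigger with a number in it.

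**Causality grades.** Section 7.11.2 has five levels: Definitely, Probably, Possibly, Unlikely and Not Related. Probably Related requires, among other conditions, that the event "follows a clinically reasonable response on withdrawal (dechallenge". Definitely Related has a parallel element: "The response to withdrawal of the drug (dechallenge) should be clinically plausible".

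**Severity.** Section 7.11.1 opens: "For AEs not included in the protocol defined grading system, the following guidelines will be used to describe severity". It then defines Mild, Moderate and Severe, without numbers. No other grading system appears in the protocol as provided.

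**IRB reporting.** Section 7.10.3 defines an Unanticipated Problem by three criteria, one of which is that the event is related or possibly related to the research. Section 7.12.1 requires a report within 5 working days of unanticipated problems, including adverse events that are unexpected and related. Under that item it defines related as more likely than not caused by the research procedures.

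**The concern.** A halting rule should lead any two readers to the same action. This one names a single causality grade, without wording such as 'at least', and passes over the grade above it. It also fixes severity by a number that the severity section does not use. Someone counting events exactly as written would leave out those most clearly caused by the device.

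The reporting rule has a similar weakness. One section says which events are Unanticipated Problems. The section that sets the deadline applies a stricter causal test, and no sentence says which governs.

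At stake is consistent handling of safety events in what the protocol describes as the first use of this technique in schizophrenia. Section 2.4.1 itself recognises that sonication might worsen symptoms.

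**Working it through.** The documents attach no stopping probability, error rate or expected event rate to the halting rule, so there is no figure to reproduce. The check is a comparison of texts.

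**1. Counting under 7.14.** Take grade 3 to mean Severe, and count only the named causality grade (literal) or that grade and above (repaired). The threshold is three.

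| Severe events observed | Literal count | Literal halt? | Count if at least probably related | Repaired halt? |
|---|---|---|---|---|
| 3 Probably | 3 | yes | 3 | yes |
| 2 Probably + 1 Definitely | 2 | no | 2 + 1 = 3 | yes |
| 3 Definitely | 0 | no | 3 | yes |

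The literal rule gives its weakest response to the strongest causal evidence. That cannot be the intention.

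**2. Severity label.** Section 7.14 needs a grade 3. Section 7.11.1 has three ordered words, of which Severe is the third. Equating the two is natural, but the protocol does not do so, and 7.11.1 refers to a separate grading system that the text does not contain.

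**3. Reporting threshold.** Consider an unexpected event that suggests greater risk and is possibly, but not more likely than not, caused by the research.

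- Under 7.10.3 it is an Unanticipated Problem, because a reasonable possibility of causation is enough.
- Under 7.12.1, the item begins with unanticipated problems as a class, which points to a report within 5 working days.
- Under the definition of related within that same item, the event fails the causal test, which points the other way.

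The statement in 7.11.2 that the causality rating does not decide what is reported in the study does not settle this. It concerns AE documentation, whereas 7.12.1 has its own explicit causal test for the IRB deadline. Nor does it affect 7.14, which uses the causality grade directly.

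**4. Dechallenge wording.** Exposure is short: "The exposure uses ten 30 sec blocks of PLIFUS sonication with 30 sec rests in-between spread over ten minutes" (Section 2.1.4). Once a session is complete there is no continuing treatment to withdraw. Withdrawal still has a meaning in two cases. Under Section 2.4.1 the team "will stop the procedure if symptoms worsen by more than 50% on AHRS and DESA". Under Section 6.1.7, if no effect is detected in the first 12 completers, "the dose will be changed to three administrations spaced over 5 days", which leaves intervals between sessions. The wording is a poor fit, but it can be applied.

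**The case against.** The strongest reply is that no sensible safety officer would count three probably related events and ignore three definitely related ones. Section 7.11.2 presents the categories as degrees of certainty, so Probably reads as a floor. Severe is plainly the third of three levels. Section 7.11.1 describes severe events as usually life-threatening or incapacitating, so most would also be SAEs, and Section 7.13 sends all SAEs to the DSMB in real time whatever their cause. Section 7.15 gives the DSMB unblinded safety data and lets it halt for safety, and Section 5.9 separately allows suspension for unacceptable risk. On reporting, 7.12.1 names Unanticipated Problems as the class, 7.10.3 defines that class, and 7.12.1 describes the institution's own requirements.

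Most of this stands, and it is why the point is minor. It does not remove the defect. Severe and serious are separate classifications. For a severe event that is not serious, the 24-hour notice in 7.14 is the stated fast route to the DSMB. The sensible reading should therefore be the written one.

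A reader might go further and infer that the dechallenge test puts Probably Related out of reach after a completed session, so that the halt could never fire. The documents do not support that. Section 7.11.2 calls the categories guidelines and rests causality on timing and clinical judgment. The end of a session can serve as withdrawal, and a reasonable response is not the same as resolution. Possibly Related turns on other contributing factors, not on a failed dechallenge, and can later be upgraded.

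**Conclusion.** The point holds as a minor error of wording. Section 7.14, read literally, omits definitely related events and relies on an undefined grade 3. Sections 7.10.3 and 7.12.1 set conflicting causality thresholds for a possibly related Unanticipated Problem.

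No magnitude is claimed. For the halting rule, the documents give no rate of severe related events and no indication of how raters would grade them, so any probability of a missed halt would rest on assumption. For reporting, a reader might subtract the 5-working-day route (about 7 calendar days) from the 6-monthly or annual reports in 7.15 and infer a delay of 183 − 7 = 176 or 365 − 7 = 358 days. Those are worst-case intervals, not expected delays. They assume that an Unanticipated Problem is handled only as a tabulated AE, that it occurs just after a report, and that the new-information item in 7.12.1, the DSMB minutes sent to the IRB and DSMB action all miss it.

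The conclusion assumes that no grading scale elsewhere in the study documents defines grade 3. If one does, that part reduces to a missing cross-reference.

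**What to change.** - **Section 7.14:** keep the threshold of three, but count Severe AEs (grade 3, as defined in 7.11.1) rated at least probably related, meaning Probably or Definitely Related.
- **Section 7.12.1:** add a study-specific sentence that any event meeting the 7.10.3 definition, including a possibly related one, is reported to the IRB within 5 working days. An added sentence is preferable to rewriting, because the section sets out the institution's own rules.
- **Optional, Section 7.11.2:** mark the dechallenge wording 'if applicable'. Keep the existing requirements that other causes be ruled out (Definitely) or unlikely (Probably), because they separate the two grades and matter in patients with continuing psychosis.

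The cost is two wording edits, or three with the optional one, and IRB approval of the amendment. No data collection, sample size or analysis changes. The only downside is that a few more events may count toward the halt or need a prompt report.

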7.11.3 Expectedness

[name] will be responsible for determining whether an AE is expected or unexpected. An AE will be considered unexpected if the nature, severity, or frequency of the event is not consistent with the risk information previously described for the study device.

7.12 Time Period and Frequency for Event Assessment and Follow-Up

The occurrence of an AE or SAE may come to the attention of study personnel during study visits and interviews of a study participant presenting for medical care, or upon review by a study monitor. All AEs including local and systemic reactions not meeting the criteria for SAEs will be captured on the appropriate CRF. Information to be collected includes event description, time of onset, clinician's assessment of severity, relationship to study product (assessed only by those with the training and authority to make a diagnosis), and time of resolution/stabilization of the event. All AEs occurring while on study must be documented appropriately regardless of relationship. All AEs will be followed to adequate resolution.

Any medical condition that is present at the time that the participant is screened will be considered as baseline and not reported as an AE. However, if the study participant's condition deteriorates at any time during the study, it will be recorded as an AE. UPs will be recorded in the data collection system throughout the study.

Changes in the severity of an AE will be documented to allow an assessment of the duration of the event at each level of severity to be performed. AEs characterized as intermittent require documentation of onset and duration of each episode.

The PI will record all reportable events with start dates occurring any time after informed consent is obtained until 7 (for non-serious AEs) or 30 days (for SAEs) after the last day of study participation. At each study visit, the investigator will inquire about the occurrence of AE/SAEs since the last visit. Events will be followed for outcome information until resolution or stabilization.

All unresolved adverse events should be followed by the investigator until the events are resolved, the subject is lost to follow-up, or the adverse event is otherwise explained. At the last scheduled visit, the investigator should instruct each subject to report any subsequent event(s) that the subject, or the subject's personal physician, believes might reasonably be related to participation in this study. The investigator should notify the study sponsor of any death or adverse event occurring at any time after a subject has discontinued or terminated study participation that may reasonably be related to this study. The sponsor should also be notified if the investigator should become aware of the development of cancer or of a congenital anomaly in a subsequently conceived offspring of a subject that has participated in this study.

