7.2.5 Final Study Visit (Day 14-16) (may be remote)*

- AHRS and DESA
- SAFTEE & addendum
- C-SSRS
- BPRS

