
17 Attachments

These documents are relevant to the protocol, but they are not considered part of the protocol. They are stored and modified separately. As such, modifications to these documents do not require protocol amendments.

- Device Manual attached

18 Schedule of Events

Activity	Screening Visit [Day -30 to -1]	MRI Visit [Day -30 to -1]	Intervention 1 [Day 0]	Intervention 2 [Day 7, 6-8]	Follow-up [Day 14, 13 to 15]
Study team procedures					
Consent	X				
Medical History	X				
Physical Exam	X				
Vital Signs	X				
Psychiatric History	X				
Psychiatric diagnosis (SCID)	X				
Demographics	X				
BPRS	X				X
PSYRATS			X	X	
BPAQ	X				
AHRS			X	X	
MoCA	X		X	X	
DESA			X	X	

CGI	X		X	X	
Experimental intervention					
Randomization		X			
PLIFUS or sham			X	X	
Safety Assessments					
SAFTEE & addendum			X	X	X
C-SSRS	X		X	X	X
Medical/psychiatric assessment			X	X	X
Imaging Assessments					
Structural MRI		X	X (pre and post-sonication)	X (pre and post-sonication)	
Resting state fMRI			X (pre and post-sonication)	X (pre and post-sonication)

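### The 30-day SAE recording window runs at least 20 days past the last scheduled contact, and the only instruction for that period is filtered by perceived relatedness, so capture is not assured

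*Combined protocol and SAP*

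**What the plan says.** Section 7.12 sets the length of the recording period, which runs "until 7 (for non-serious AEs) or 30 days (for SAEs) after the last day of study participation". Its scope and starting point are given as follows: "The PI will record all reportable events with start dates occurring any time after informed consent is obtained". Active questioning is tied to visits: "At each study visit, the investigator will inquire about the occurrence of AE/SAEs since the last visit". The section also says that events may come to light "during study visits and interviews of a study participant presenting for medical care, or upon review by a study monitor".

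The last scheduled contact is "Final Study Visit (Day 14-16) (may be remote") in Section 7.2.5, while the table in Section 18 gives "Follow-up [Day 14, 13 to 15"]. Section 8 likewise ends contact 7 days after each treatment period. No later visit or call appears anywhere.

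For the time after the last visit, Section 7.12 tells the investigator to instruct each participant to "report any subsequent event(s) that the subject, or the subject's personal physician, believes might reasonably be related to participation in this study". The accompanying duty on the investigator to notify the sponsor of later events is also limited to those that may reasonably be related. Section 7.11.2, by contrast, says that the psychiatrist's view of relatedness does not determine what is reported.

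**The concern.** The recording window and the means of filling it do not match. The investigator must record SAEs for 30 days after participation, but after the Final Visit nobody is scheduled to ask about them. What participants are told to volunteer depends on a judgement about cause that Section 7.11.2 keeps out of the reporting decision.

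Safety and tolerability are part of the primary objective (Section 3.1). Section 2.2.2 says that PLIFUS has not, to the authors' knowledge, been studied in schizophrenia, and Section 2.4.1 names worsening of symptoms as a possible harm. An admission for relapse is an SAE under Section 7.10.2. It is also an event that a participant or treating physician could easily attribute to the illness and so not report. With 12 completers, one missed admission is 1/12, or about 8% of them, so a single omission changes a descriptive safety summary.

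**Working it through.** The plan gives no figure to reproduce; the check is a comparison of calendar days, with Intervention Visit 1 as Day 0.

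Inputs:
- Second session: Day 6-8 (Section 7.2.4).
- Final Visit: Day 14-16 (Section 7.2.5) or Day 13-15 (Section 18).
- Window: 7 days for non-serious AEs and 30 days for SAEs after the last day of participation (Section 7.12). That day is not defined, so both natural readings are worked.

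Formulas: window end = last day of participation + 7 or + 30; uncovered days = window end − day of Final Visit.

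**Reading A: participation ends at the Final Visit.**
- Final Visit on Day 14-16: AE window ends on Day 14+7 to 16+7 = Day 21-23; SAE window on Day 14+30 to 16+30 = Day 44-46.
- Final Visit on Day 13-15: AE window ends on Day 20-22; SAE window on Day 43-45.
- By construction, all 7 AE days and all 30 SAE days fall after the last scheduled contact.

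**Reading B: participation ends at the second session.**
- AE window ends on Day 6+7 to 8+7 = Day 13-15, which is about when the Final Visit takes place. There is essentially no AE gap.
- SAE window ends on Day 6+30 to 8+30 = Day 36-38.
- Uncovered SAE days after a Day 14-16 visit: 36−16 = 20 to 38−14 = 24, or 20/30 = 67% to 24/30 = 80% of the window.
- After a Day 13-15 visit: 36−15 = 21 to 38−13 = 25.

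On both readings at least 20 days of the SAE window have no scheduled contact. The AE gap depends on the reading.

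Next, how an SAE with onset in those days could reach the investigator:
- **Asked at a visit:** not available, because no visit remains.
- **Volunteered:** only if the participant or personal physician believes it might be related.
- **Participant presenting for medical care, or monitor review:** possible, but passive; neither route puts the question to every participant.

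A new SAE after the Final Visit that participant and physician both put down to the illness, and that does not surface by a passive route, goes unrecorded although it falls within the stated window.

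These day counts apply to the single-session design. Sections 7.2 and 18 set out no separate calendar for the four possible three-session participants.

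**The case against.** The strongest reply is that the two rules can coexist. One is a time-limited duty on the investigator to record; the other is an open-ended request to participants. This is fair, and the duty to record does stand. But the request takes effect at the last visit, so it overlaps the window, and no unfiltered instruction covers those days.

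A second reply is that the events to be recorded are only those reportable to the IRB under Section 7.12.1, where adverse events must be unexpected and related. The term is not defined in Section 7.12, so this cannot be excluded, and it would weaken the conflict. The separate periods for non-serious AEs and SAEs, together with Section 7.11.2, point instead to general capture.

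Third, most of the risk period is well covered. Symptom scales, SAFTEE and C-SSRS are repeated at about 1 and 7 days after each session, the BPRS is repeated at the end, and Section 2.4.1 expects any worsening to be transient. Events after the Final Visit also follow both crossover conditions and add little to the PLIFUS-sham contrast. This stands and limits the importance of the point.

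A reader might go further and infer any of the following, which the documents do not support:
- **That the window is simply not delivered, or that only participants' own beliefs count.** The physician's belief and the passive routes also count.
- **That "All AEs occurring while on study must be documented appropriately regardless of relationship" directly contradicts the last-visit instruction.** That sentence covers events while on study. The tension is with Section 7.11.2.
- **That the whole 7-day AE extension is certainly uncovered.** This is true only under Reading A.
- **That a planned claim of no SAEs through 30 days is undermined.** No such claim is planned; Section 9 summarises safety descriptively.

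**Conclusion.** The concern holds as a gap in assurance. The stated SAE window has no scheduled contact for all 30 days if participation ends at the Final Visit, and for about 20 to 24 days (67% to 80%) after a Day 14-16 visit if it ends at the last session. Over that time capture is passive and filtered by perceived relatedness, which is at odds with Section 7.11.2. The 7-day AE window shares the gap only on the first reading.

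The conclusion assumes that the events to be recorded are AEs and SAEs generally. The documents do not allow an estimate of how many events would be missed. Sample size, the primary endpoint and the planned comparisons are unaffected; what is affected is the completeness of the descriptive safety data, with possible bias against events attributed to the illness. It is worth correcting because correction is cheap.

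**What to change.** - Reconcile Sections 7.11.2 and 7.12: the last-visit instruction should ask participants to report every SAE in the stated window, such as any hospitalisation, whatever they think caused it. The open-ended request about possibly related events can remain for the time beyond.
- Add one brief remote call at the end of the SAE window, asking about all AEs and SAEs with onset in their respective windows. Enter it in Sections 7.2 and 18.
- Use a chart check only as a supplement. Manhattan Psychiatric Center charts are in a separate system (Section 5.5.3), and people recruited online (Section 5.5.5) may have no EPIC record.
- Define the last day of participation and the events to be recorded, and align the Final Visit window (Day 14-16 against Day 13-15).

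The window should not be shortened to end at the Final Visit: that would remove an existing duty to record SAEs that the investigator learns of later.

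The cost is one short call for each of about 12 to 16 participants; WebEx is already used for remote visits. Deletion of numbers and messages from the staff texting phone at the end of a participant's study (Section 7.1.1) need not prevent the call, since Section 12.4 has contact details stored separately.
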